8.4 STATISTICAL ANALYSES

8.4.1 GENERAL APPROACH

- We will use chi-square tests, Analysis of Variance (ANOVAs), logistic regression, and means/medians for descriptive statistics.
- We will use a 0.05 cutoff for p-values and 95% confidence intervals for statistical significance.

- Our primary statistical analysis will be a two-sided Z test. We will also compare the baseline characteristics of those subjects across both arms to ensure there are no major differences. All enrolled patients will be analyzed.
- We will check for normality and log-transform variables if necessary for skewed distributions.
- We will calculate all-cause unplanned post-discharge utilization within a 30-day period from the date of discharge from an index admission. Post-discharge utilization will include emergency department visits, observation stays, and inpatient readmissions. Planned readmissions will be excluded using the Centers for Medicare and Medicaid's Planned Readmissions Algorithm. The algorithm assesses a dichotomous yes or no outcome of whether each admitted patient has any unplanned readmission within 30 days. In accordance with the CMS algorithm, if a patient has more than one unplanned admission within 30 days of discharge from the index admission, only the first is considered a readmission. If the first readmission after discharge is planned, any subsequent unplanned readmission is not considered in the outcome for that index admission because the unplanned readmission could be related to care provided during the intervening planned readmission rather than during the index admission.

8.4.2 ANALYSIS OF THE SECONDARY ENDPOINT(S)

To assess the *Reach* of the intervention, we will examine differences in effectiveness across sites, and for patients of different ages, sex, medication literacy, taking different numbers of medications, and living in zip codes reflecting different median incomes. We hypothesize that the intervention will work best to prevent readmissions, will work equally at both sites, will work better for older patients, those with higher medication literacy, those taking more medications, and those from poorer zip codes. We will also explore effectiveness of the intervention before and after historical changes to the intervention and control groups, as well as when the primary outcome is restricted to include only medication-related post-discharge utilization or 7-day post-discharge utilization. However, we recognize that these underpowered analyses may be most useful for shaping future hypotheses. To ensure that no results are misinterpreted, we will report that any negative results may be due to inadequate power.

The descriptive phase of analysis will include an assessment of the distributions and correlations of the aforementioned variables of interest. We will use logistic regression to examine these factors. We will also examine the potential interaction of covariates. We will explore collinearity using the condition index and with careful assessment of the correlation matrix.

8.4.3 QUALITATIVE ANALYSES

For the qualitative analysis of interviews and focus groups, we will combine a content-analysis approach with qualitative inquiry allowing us to discover and quantify key stakeholders' experiences and perceptions. We will use an iterative process to identify "a priori" themes based on the domains in the RE-AIM framework and to create "in vivo" themes as they emerge during coding (e.g., specific barriers to PHARM-DC implementation).^{xxii} Two coders will code each interview independently and then discuss variations until consensus is reached. After coding all interviews, we will use the constant comparative method to combine similar themes with limited

data under more general themes.¹¹⁰ We will use NVivo software which will allow for quantifying the number of key stakeholders who addressed these themes and their density (i.e., number of overall mentions). Theme density is a valid proxy for importance. In the final step of the qualitative analysis, we will prepare NVivo code reports (participant N and density) of salient themes and coding matrices related to significant interview findings. We will perform follow-up interviews as needed to supplement or clarify themes. We will also prepare descriptive statistics of all interview and focus group participants.

We will take several measures to ensure rigorous analysis. All transcripts will be independently analyzed by [name] and two other researchers who will meet weekly during the qualitative analysis process to discuss each transcript and resolve disagreements through negotiated consensus.^{xxxiii} Analysts will also maintain an audit trail throughout this process to document the fit between the raw data and the conclusions drawn. NVivo software will be used to code patterns among sites and individuals, and to code variations within and between key stakeholders. We will later triangulate survey results with interviews, focus groups, and on-site observations to better understand the impact of context on the experiences of key stakeholders.

Finally, after conducting initial qualitative and quantitative analyses, we will use a mixed methods approach to further explore relationships between contextual factors, interventions, and outcomes.^{xxxiv} Qualitative and mixed methods may be especially important if there are any differences between the two sites RCT outcomes and to develop hypotheses regarding possible reasons for our findings.

8.4.4 COST-EFFECTIVENESS ANALYSES

Costs are a critical consideration for health system leaders deciding to adopt an intervention, as noted by the RE-AIM model. Because the leadership at different hospitals may consider different factors when deciding whether to fund the PHARM-DC intervention, we will report the cost of implementing the PHARM-DC intervention in two ways: (1) the program costs per utilization event (readmission, observation stay, or ED visit) averted and (2) the incremental net cost from the health system perspective.

Program Cost: The primary program cost will be the ongoing labor of the pharmacists who implement it. Startup costs will be minimal because hospital pharmacists can be trained to use the PHARM-DC Toolkit in only 1-2 hours, and no purchases of equipment or supplies are needed.

We will ascertain pharmacist labor costs through a micro-costing approach employing accepted time and motion methodology used in our previous work.^{xxxv-xxxix} Our published data collection tool, which was developed for admission medication histories, categorizes time spent on discussions with patients, family members, and caregivers, utilizing secondary resources (obtaining prior prescription and fill information), and utilizing the electronic health record to obtain, document, and communicate information.^{xl} We will add categories pertinent to post-discharge medication management (e.g., calling retail pharmacies to communicate that a medication has been stopped) and pilot the tool until all relevant activities have been categorized.

Trained observers with a clinical background (e.g., research nurses, medical students) will document time use by study pharmacists on a minute-by-minute basis in real time. The observers will use the time-use data collection tool to record time spent on PHARM-DC activities for study patients versus other activities. For PHARM-DC activities, the observer will

also record the number of days since discharge for the relevant patient (e.g., post-discharge day 4). Because pharmacists will also complete non-intervention tasks each day, observers will follow pharmacists for up to an entire workday.

To assure that the time-use data is representative, we will sample approximately 100 patient interactions (20 complete interventions, 20 discharge medication reconciliations, 20 post-discharge phone calls, and 40 observations of usual care) by study pharmacists at each study site over a one-year period. To ensure that pharmacists have become efficient in providing the intervention, sampling will only occur in years two and three and pharmacists with less than two-months experience with the intervention will be excluded.

Time spent on PHARM-DC activities for study subjects by the number of days since discharge. For example, we will identify all study subjects for which study pharmacists spent time on post-discharge day 1, etc. This will enable us to calculate the mean amount of pharmacist time necessary to provide the PHARM-DC intervention on each post-discharge day, and then the mean total time across all days. After estimating the mean total time per patient, we will apply National Bureau of Labor Statistics wage and benefit data to calculate the intervention's program cost per patient².

Next, we will calculate the mean program cost necessary to avert each measured utilization event (e.g., readmission) by multiplying the number needed to treat to prevent the utilization event by the cost of applying the intervention to one patient. For some hospital decision makers, we expect this data, in combination with hospital-specific costs, to be useful in deciding whether (and to what extent) to implement PHARM-DC. One example of hospital-specific costs would be anticipated HRRP costs (CMS readmissions penalties).

Costs of Post-Discharge Utilization: We will ascertain the total cost of all readmissions, observation stays, and ED visits with 30 days of discharge for all trial patients. At least 80% of patients are likely to return to the study hospitals; in this case, we will obtain charge data for the return visits and apply hospital-specific cost-to-charge ratios provided by hospital administrators. For return visits to outside hospitals, we will obtain charges for inpatient hospitalizations and ED visits using statewide data sets and calculate costs by applying cost-to-charge ratios for hospital services published by the Centers for Medicare and Medicaid Services.

Net Costs: Next, we will calculate net cost for each patient from the health system perspective by subtracting the cost of any post-discharge utilization from any program costs (program costs are zero in the control group). Because we will apply a 30-day time horizon, discounting will not be used. We will calculate and test differences in mean values. Finally, we will calculate the difference between the intervention and control group to estimate incremental net costs per patient from the health system perspective.

8.4.5 SECONDARY DATA ANALYSIS: EXAMINE EFFECTS OF PHARM-DC INTERVENTION ON INITIATION AND DEPRESCRIBING OF BENZODIAZEPINE-RECEPTOR AGONISTS

The following secondary analyses of trial data are planned to examine effects of the PHARM-DC intervention on (1) the initiation of new outpatient prescriptions of benzodiazepine-receptor agonists (BZRs) and (2) the deprescribing of BZRs among patients taking BZRs prior to hospitalization:

1. Among patients without a BZR prescription on admission, we will examine the difference in adjusted predicted probability of having a new BZR prescriptions from admission to discharge

between the intervention group and the control group. We will use logistic regression using a generalized estimating equations approach and estimate adjusted predicted probabilities.³ We hypothesize that among patients without a BZR prior to hospitalization, the risk-adjusted probability of having a new discharge BZR prescription will be substantially lower (e.g. 35% lower) among patients who are enrolled in the PHARM-DC intervention compared to the control group.

2. Among patients taking BZRs prior to hospitalization, we will use logistic regression to estimate the adjusted predicted probability of dose intensification among patients in the PHARM-DC intervention and the control group.³ We hypothesize that among patients with BZRs prior to hospitalization, the risk-adjusted probability of experiencing a dose increase will be substantially lower (e.g. 35% lower) among patients who are enrolled in the PHARM-DC intervention compared to controls.

Outcome measures: We will create two measures: (1) a dichotomous variable for a new discharge prescription of BZRs among patients not taking BZRs prior to admission, and (2) a dichotomous variable for an increased dose prescription among patients taking BZRs prior to admission.

8.4.6 SECONDARY DATA ANALYSIS: EXAMINE EFFECTS OF PHARM-DC INTERVENTION ON FALL-RELATED INJURIES AMONG OLDER ADULTS WITH ALZHEIMER'S DISEASE AND RELATED DEMENTIAS

The following secondary analyses of trial data are planned to examine effects of the PHARM-DC intervention on post-hospitalization fall-related injuries among all trial participants and among the subgroup of older adults with Alzheimer's disease and related dementias (ADRD):

1. We will investigate whether the intervention reduces the severity of fall-related injuries by using a two-sided Z test to compare the proportions of severe injuries (e.g., hip fractures) and acute care utilization (hospitalization and ED visits) between the intervention and control groups. We hypothesize that the PHARM-DC intervention reduces the severity of fall-related injuries by mitigating medication-related risk factors.
2. We will use a two-sided Z test to compare the proportion of those who have post-hospitalization healthcare utilization for fall-related injuries within 30 days among all trial participants and among individuals with ADRD. We hypothesize that the PHARM-DC intervention reduces fall-related injuries among individuals with ADRD. We also hypothesize that the benefit of the intervention is larger among individuals with ADRD compared to individuals without ADRD by addressing both general and ADRD-specific medication-related risk factors for falls.
3. We will examine the effect of the intervention among individuals with dementia with Lewy bodies (ICD-10-CM code: G31.83) and individuals with an ADRD diagnosis code associated with the ICD-10-CM code for Parkinson's disease (G20), because previous literature suggests that they have a much higher incidence of fall-related injuries, as compared to individuals with Alzheimer's disease.⁴
4. We will describe the difference in the nature of falls among individuals with and without ADRD using external causes of morbidity codes (e.g., falls from bed vs. falls while walking).

Variables: We will check for balanced demographics and comorbidities across arms in all analyses. In cases with imbalance, we will consider post-hoc adjustment, including by considering sex as a biological variable. Individuals with ADRD will be identified by the ICD-10-CM codes based on hospital claims, adapting the algorithm from the Chronic Conditions Data Warehouse.⁵

Outcome measures: We define post-hospitalization fall-related injuries as healthcare utilization (hospitalization, ED visits, urgent care visits, or office visits) due to fall-related injuries within 30 days of discharge of the index admission. We will link Medicare claims data to trial data to track this outcome at the individual patient level. In order to link Medicare claims data to trial data, linking variables for trial participants will be requested through the Honest Enterprise Research Broker (HERB) Committee at Cedars-Sinai and will include: (1) social security numbers (SSNs), (2) Medicare Beneficiary Identifiers (MBIs), and (3) Medicare Health Insurance Claim Numbers (HICNs). We anticipate data may be missing on linking variables for some participants (e.g., patients without an SSN number), and therefore, will request patient age, SSNs, MBIs, and HICNs to ensure data for all participants can be linked to claims data. The same linking variables in (1)-(3) will be requested from the Brigham and Women's Hospital site and uploaded to a password-protected Box folder hosted on the Cedars-Sinai network (for further details, see section 9.1.5.1 DATA COLLECTION AND MANAGEMENT RESPONSIBILITIES). Linking variables for participants at both study sites will be mailed on a flash drive to the Centers for Medicare & Medicaid Services (CMS) based on their submission requirements for requesting claims data. Medicare claims data will subsequently be sent from CMS to the study team at Cedars-Sinai on a flash drive through postal mail.

Sensitivity analysis: It is possible that we under-detect individuals with ADRD diagnoses if the ADRD diagnoses are not coded diligently on hospital claims. To mitigate this issue, we will conduct a sensitivity analysis by using electronic health record (EHR) data prior to the index admission, so that we can include those who were diagnosed with ADRD in the outpatient setting. Because this can only be done for patients who receive outpatient care from doctors using our EHR, it would introduce bias if used as part of the overall analysis. However, it can be done among this group to test the sensitivity of detecting ADRD via claims.

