- b. Inclusion Criteria: Pharmacists participating in the PHARM-DC intervention actively seeing patients and responsible for generating the majority of documentation for the clinical visit
- c. The observers will use the data collection tool to record time spent on PHARM-DC activities for study patients versus time spent on activities for patients receiving usual care. A trained member of the study staff will shadow participating pharmacists continuously for 4-8 hours during a clinical shift, using an online application (TimeCaT version 3.9, available at lopetegui.net/timecat/39/login/) to note the nature of activities the pharmacist performs and the beginning and ending times of each activity. The TimeCat application requires username and password login, will be installed on a Cedars-Sinai issued iPad, and will only be accessed on the site's secure internet network. The observations will take place in the two sites where the pharmacists conduct their regular activities. Observations may include patients/caregivers. The pharmacists will be given an updated information sheet (for Study 3) that describes these activities. Patients will be told that this is part of an ongoing study examining pharmacist activities.
- d. Patients will be assigned a random unique identifier within the TimeCaT application so that no PHI is transmitted over the internet. This will enable the observer to record pharmacist activities performed at the patient level (i.e., per patient). The observer will record the patient MRN, CSN, and unique identifier in a linking file stored separately on Box (<https://cedars.app.box.com>), along with the number of days since discharge for the relevant patient (e.g., post-discharge day 4).
- e. To assure that the time-use data is representative, we will sample approximately 100 patient interactions (20 complete interventions, 20 discharge medication reconciliations, 20 post-discharge phone calls, and 40 observations of usual care) by study pharmacists at each study site over a one-year period.
- f. To ensure that pharmacists have become efficient in providing the intervention, sampling will only occur in years two and three and pharmacists with less than two-months experience with the intervention will be excluded.

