- c. **Post-discharge assistance with obtaining medications**, including drug assistance programs (for reduced pricing) and linkage with community or social service organizations;
- d. **Pharmacist communication with key inpatient and outpatient providers** (e.g., PCPs; skilled nursing facilities; inpatient rehabilitation hospitals, including the California Rehabilitation Institute) to ensure that they understand changes to their patient's discharge medication regimen, including why those changes were made and recommended actions to take. This includes requesting Medication Administration Records (MAR) from downstream providers to facilitate this type of communication;
- e. **Communication with each patient's pharmacy** to ensure the pharmacy has an updated medication list, with focus on newly discontinued medications, and to encourage patient education as needed when patients fill their prescriptions;
- f. **Use of illustrated pill cards, pillboxes (traditional and electronic), and other tools** to help patients with low literacy better understand and adhere to their medication regimens;
- g. **Health information technology such as patient portals and texting** chatbots to facilitate communication between patients, pharmacists, and other providers after discharge;
- h. **Home pharmacist visits for high-risk patients** to educate them and to identify and manage challenges to safe medication use.

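### Program cost is defined as pharmacist time times wages, with no term for the supplies, technology and travel that the tailored intervention may use; if the health system pays for any of them, program cost and cost per event averted are too low.

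*Combined protocol and SAP*

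**What the plan says.** Section 8.4.4 (Program Cost) states: "The primary program cost will be the ongoing labor of the pharmacists who implement it". On startup it says: "Startup costs will be minimal because hospital pharmacists can be trained to use the PHARM-DC Toolkit in only 1-2 hours", and the same sentence ends by saying that "no purchases of equipment or supplies are needed". Once mean total time per patient has been estimated, "we will apply National Bureau of Labor Statistics wage and benefit data to calculate the intervention's program cost per patient". That figure is multiplied by the number needed to treat to give program cost per event averted. It also enters each patient's net cost, where the control arm's program cost is fixed at zero.

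Section 6.1.1, item 4, lists what pharmacists may add after assessing a patient's needs. The list includes "Use of illustrated pill cards, pillboxes (traditional and electronic), and other tools", patient portals and texting chatbots, and "Home pharmacist visits for high-risk patients".

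On measurement of time, section 1.3, part (3)c, says: "The observations will take place in the two sites where the pharmacists conduct their regular activities". The same item restricts the timing application to the site's own network. Sections 1.3 and 8.4.4 give the sample per site as 20 complete interventions, 20 discharge reconciliations, 20 post-discharge calls and 40 observations of usual care.

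**The concern.** The costing rule has one kind of input, pharmacist time. Pillboxes are supplies, an electronic pillbox is equipment, a chatbot may carry a license or message fee, and a home visit involves travel. Sections 6.1.1 and 8.4.4 therefore do not describe the same program.

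Aim 3 exists to tell hospital leaders what the program costs. Section 2.1 blames a weak business case for the limited use of such services, and section 8.4.4 treats cost as central to a decision to adopt. A cost per event averted that leaves out items the health system pays for would make PHARM-DC look cheaper than it is to those readers.

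**Working it through.** **1. The plan's own figure.** The documents state no dollar amount for program cost. The only stated figures that feed the calculation are the planning effect and sample size in section 8.2: 4,888 per group, 80% power, two-sided 0.05, 27.5% against 25.01%. The usual formula with pooled variance under the null is

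n = [1.960·√(2·p̄·(1−p̄)) + 0.842·√(p₁(1−p₁) + p₂(1−p₂))]² / (p₁−p₂)²

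With p₁ = 0.275, p₂ = 0.2501 and p̄ = 0.26255 it gives 4,901 per group, 0.3% above the stated number. Power at 4,888 is 79.9%. The planning effect of 2.49 points is reproduced.

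**2. The multiplier.** Number needed to treat = 1/0.0249 = 40.2. Across the detectable differences in Table 5 (2.56 to 2.41 points) it runs from 1/0.0256 = 39.1 to 1/0.0241 = 41.5. Under the plan's rule,

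omitted cost per event averted = NNT × (share of patients using the item × unit cost to the health system).

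Each omitted $1 per patient therefore adds about $40. The actual calculation will use the observed effect. At half the planning effect the multiplier doubles: 1/0.01245 = 80.3.

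**3. A range.** Uptake and unit cost below are assumptions; neither is in the documents.

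| Uptake | Unit cost | Omitted per patient | Added per event averted (÷ 0.0249) |
|---|---|---|---|
| 5% | $10 | $0.50 | $20 |
| 25% | $50 | $12.50 | $502 |
| 50% | $200 | $100 | $4,016 |

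The spread is about 200-fold, so the documents cannot settle whether the omission is trivial or material.

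**4. What each listed item meets in the costing plan.**

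- Pill cards and pillboxes: no term.
- Chatbots: no term for any license or message fee. Patient portals may be existing infrastructure with no added cost.
- Home visits: the visit is pharmacist labor and so belongs to the priced category, but travel expense has no term. Visit and travel time are likely to be missed, because observation is placed at the two sites, the timing application is tied to the site network, and home visits are not a named sampling category.

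Rarity adds to the last problem. If 3% of patients had a home visit (an assumption), the 40 complete interventions sampled across both sites would include no such patient with probability 0.97⁴⁰ ≈ 0.30.

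**The case against.** The clause on purchases sits in a sentence about startup and may be right for startup; labor is called the primary cost, not the only one. Both points stand, so the clause should not be read as a claim about the whole program. They do not rescue the formula. If the clause covers startup only, ongoing supplies and travel have no provision anywhere, and no second cost component follows the primary one.

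The items are also optional. Section 6.1.1 presents them as possibilities. The toolkit contents in the synopsis are worksheets and reference material. The need-dependent extras in section 1.3, part (1)e, name neither pillboxes nor home visits, and that section allows contacts to move to the telephone because of COVID-19. Use may have been rare, and items bought by patients or insurers fall outside the health-system perspective. This stands too, and it makes the understatement conditional.

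Section 8.4.4 also plans to add categories to the timing tool, to pilot it until all relevant activities are covered, and to follow pharmacists for up to a full workday. Some home-visit time might be caught that way, so it cannot be called certainly excluded.

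A reader might infer that the program cost is definitely understated, or that incremental net cost is biased in favor of PHARM-DC. The documents support neither. The first needs uptake and a payer. The second overlooks a bias in the other direction: control patients may receive pharmacist consultation and calls when clinically needed (section 1.3, part (1)f, and section 9.1.1), yet section 8.4.4 sets their program cost to zero, which raises the incremental cost of PHARM-DC.

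**Conclusion.** The point holds in conditional form. The stated rule yields too low a program cost per patient, and too low a cost per event averted, whenever a listed item is used at health-system expense and is not captured as observed pharmacist time. The multiplier is about $40 per event averted for each omitted $1 per patient, given the planning effect of 2.49 points. The dollar size is unknown, because uptake, unit price and payer are not given. The direction of any error in incremental net cost is not established. The point concerns Aim 3 only. It deserves correction because the defect lies in the defined formula and is cheap to repair.

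**What to change.** - In section 8.4.4, limit the clause on purchases to startup costs and reconcile it with item 4 of section 6.1.1.
- Define program cost per patient as pharmacist labor, including home-visit and travel time, plus the sum over health-system-paid non-labor items (including travel expense) of quantity used × unit price. State the payer for each item.
- Take use from the pharmacist notes already reported from Epic for compliance (section 6.3), from purchasing records, or from the observed complete interventions. Nothing in the plan says supplies are recorded as countable fields, so treat undocumented use as unknown, not as zero. Report zero only where a source shows that the item was not used.
- Report a sensitivity range over plausible uptake and unit price for items that cannot be counted.

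The cost is a wording change, some extra data abstraction and a list of unit prices. The reported program cost may become slightly less favorable. Recruitment, randomization and the primary efficacy analysis do not change.

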3 OBJECTIVES AND ENDPOINTS

Primary Outcome

We chose an endpoint of 30-day post-discharge utilization as our primary outcome because the RE-AIM model points to the importance of institutional-level effectiveness and cost. We chose to power this trial on an absolute utilization reduction of 2.5% (% of patients with readmissions or ED visits within 30 days of hospital discharge) from a baseline of 27.5%.

We define this utilization in two different ways, based on what data is available. For the first analysis, we will use same-hospital utilization data. Both site PIs can electronically access inpatient admission, observation stay, and ED visit data for their health system. These three utilization types will represent the basis for the first RCT analysis (*manuscript #2 above*).

We recognize the limitations of same-hospital utilization data.^{xxx} As such, the RCT is powered on a primary endpoint of same-state 30-day hospital readmissions and ED visits (manuscript #6 above).

This utilization will be tracked with data from the Massachusetts All Payer Claims Data (APCD) database and California's Office of Statewide Health Planning and Development.^{xxxi} Because we expect little utilization in other states (discharge to another state is an exclusion criterion) and because we do not anticipate any differential effect on such utilization, we will not track it. Statewide data sources do not track observation stays, so they will be excluded from statewide analyses. However, we will conduct a sensitivity analysis projecting changes in same-hospital observation stays to the statewide analysis.

The current version of this protocol does not include information for these analyses using other data sources; we will include this information in subsequent versions through protocol/IRB amendments.

Secondary Outcomes

We will examine the endpoints in the following subgroups:

Patients:

- 1) Patient socioeconomic status (estimated via median income of home census tract);
- 2) Patient medication adherence and literacy (as assessed by study pharmacists, in addition to using limited English proficiency as a proxy for low medication literacy);
- 3) Study site;
- 4) Ten or more medications;
- 5) Three or more high risk medications;
- 6) Patient history of congestive heart failure;
- 7) By receipt of different intervention components;
- 8) Patient age groups;
- 9) Before and after historical changes to the intervention and control arms;

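### The net cost formula in Section 8.4.4 subtracts utilization cost from program cost instead of adding it, so the incremental net cost is off by twice the averted utilization cost

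*Combined protocol and SAP*

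**What the plan says.** Section 8.4.4 announces two cost results. One is the program cost per utilization event averted; the other is "the incremental net cost from the health system perspective". Both belong to Aim 3 (Section 1.2).

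The utilization costs are defined first: "We will ascertain the total cost of all readmissions, observation stays, and ED visits with 30 days of discharge for all trial patients". Charges are converted to costs with cost-to-charge ratios, so these are costs actually incurred, in both arms.

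The Net Costs paragraph works patient by patient. The operation it prescribes, with its own remark about the control arm, is "subtracting the cost of any post-discharge utilization from any program costs (program costs are zero in the control group"). It says that differences in means will be tested, and ends: "we will calculate the difference between the intervention and control group to estimate incremental net costs per patient from the health system perspective".

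The other cost result is obtained by "multiplying the number needed to treat to prevent the utilization event by the cost of applying the intervention to one patient" and does not use the net cost formula.

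**The concern.** To a health system, pharmacist time and return visits are both expenses. A patient's cost over the 30 days is their sum. Under the written rule the return visit enters with a minus sign: a readmitted control patient has a negative cost, and a more expensive readmission makes that patient look cheaper.

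The consequence for the comparison is that every dollar of utilization averted raises the reported incremental cost, and every dollar of added utilization lowers it. Section 2.1 gives the weak business case for hospital leaders as a main reason for the trial, and this result speaks directly to that case. The two Aim 3 results could also disagree in the same report, because only one of them uses the faulty formula.

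**Working it through.** **Inputs.** The rule, its application to each patient in both arms, and the zero program cost in the control arm come from Section 8.4.4. The planned effect comes from Section 3: "We chose to power this trial on an absolute utilization reduction of 2.5" percentage points, from 27.5%, so 25.0% in the intervention arm. The documents give no dollar amount for program cost or utilization cost and no worked net cost, so there is no figure of the plan's own to reproduce. All dollar values below are assumptions.

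**Algebra.** Let P be the mean program cost per intervention patient, U_int and U_ctl the mean utilization cost per patient in each arm, and A = U_ctl − U_int.

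- As written: (P − U_int) − (0 − U_ctl) = P + A
- With both costs added: (P + U_int) − (0 + U_ctl) = P − A
- Error: (P + A) − (P − A) = 2A

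This holds for any cost values. Taking control minus intervention gives −(P + A), so arm order does not repair it.

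**Size at the planned effect.** Let C be the mean cost per patient with utilization, assumed equal in both arms. Then A = (0.275 − 0.250) × C = 0.025 × C and the error is 0.05 × C: $100 at C = $2,000, $250 at $5,000, $500 at $10,000 and $750 at $15,000.

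Incremental net cost per patient, as written / correct:

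| C | P = $50 | P = $100 | P = $200 | P = $500 |
|---|---|---|---|---|
| $2,000 | 100 / 0 | 150 / 50 | 250 / 150 | 550 / 450 |
| $5,000 | 175 / −75 | 225 / −25 | 325 / 75 | 625 / 375 |
| $10,000 | 300 / −200 | 350 / −150 | 450 / −50 | 750 / 250 |
| $15,000 | 425 / −325 | 475 / −275 | 575 / −175 | 875 / 125 |

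The sign is reversed in 8 of the 16 cells. One cell is a true break-even reported as a $100 cost. In the other 7 the sign is right and the cost is overstated by $100 to $750. The sign reverses only where P < 0.025 × C.

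**One cell in full** (C = $10,000, P = $100).

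- Utilization cost per patient: 0.25 × 10,000 = $2,500 in the intervention arm and 0.275 × 10,000 = $2,750 in the control arm.
- As written: arm means 100 − 2,500 = −$2,400 and 0 − 2,750 = −$2,750; difference +$350.
- Correct: arm means 100 + 2,500 = $2,600 and $2,750; difference −$150.
- Cross-check with the other Aim 3 result: the number needed to treat is 1/0.025 = 40, so the program cost per event averted is 40 × 100 = $4,000. If each such patient has one event, this is below the $10,000 cost of an event. That agrees with the $150 saving and contradicts the $350 loss.

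**Other directions of effect** (same C and P). If utilization rose to 30.0%, A = −$250: the written rule gives 100 − 250 = −$150, an apparent saving, and the correct result is 100 + 250 = +$350. If utilization did not change, both give +$100.

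**The test of means.** If every intervention patient is given the same program cost (mean time multiplied by a wage), P − U and P + U have the same variance. The standard error is then unchanged while the estimate moves by 2A, so the test is wrong as well.

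**The case against.** The strongest reply is that this is a drafting slip. Program cost minus *averted* utilization cost is a correct group-level formula, and the word incremental suggests that this was meant. An analyst who followed the text literally would probably see two negative arm means and stop. That is plausible and lowers the chance of a wrong published result. But the text subtracts the cost of any utilization, patient by patient, and the remark about the control group shows that the rule applies in both arms. Averted cost cannot be observed for a single patient. No other section gives a different formula.

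Two points about the illustration stand. The dollar grid is assumed, so 8 of 16 says nothing about how likely a reversal is; only the error of 2A follows from the documents. And the trial is powered on patients with any utilization, while Section 8.4.4 costs all events, so the comparison of 40 × P with the cost of an event is exact only with one event per patient. Neither point touches the sign error.

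It is also true that the damage is confined to one result of one aim and can be repaired at any time before the cost analysis.

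**Conclusion.** The concern holds. The formula as written is arithmetically wrong, and gives a wrong incremental net cost whenever mean utilization cost differs between the arms. The error is exactly twice the averted utilization cost and needs no assumption about prices. At the planned effect, with equal cost per patient with utilization in both arms, it is 5% of that cost for every patient. The sign of the conclusion is wrong only if the change in utilization cost exceeds program cost; otherwise the net cost is overstated when utilization falls and understated when it rises. The primary endpoint, randomization, sample size and program cost per event averted are not affected.

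**What to change.** In the Net Costs paragraph of Section 8.4.4, define each patient's net cost as program cost **plus** post-discharge utilization cost, in both arms. Define incremental net cost as the intervention mean minus the control mean, and state that a negative value is a saving. This is one change of wording. It needs no new data and alters no other analysis, but it should be made before the cost analysis is run.

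Two clarifications could go into the same amendment, though neither is an error: whether pharmacist time spent in usual care is netted out of program cost, and which patients form the denominator for mean time on each post-discharge day.
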